We will utilize a randomized control design consisting of one treatment arm and a control arm. African American and Latinx patients who did not complete COVID-19 testing or vaccination will be recruited from the patient list obtained from Aim 1 data pull of the LACDHS EHR. The patient list obtained by the data pull will be filtered by the patient list provided by the LACDHS Vaccine Hesitancy Outreach Group. Based on the inclusion criteria, we will recruit a total of 142 patients to allow for approximately 10% attrition from each group. Patients who meet the inclusion criteria and agree to participate in the 2-month intervention will be randomly assigned to either the intervention or control arm.

We will stratify the randomization on the basis of race/ethnicity and we will use permuted blocks (**see table 3**). We will use a scheme such as found at randomization.com. Here we will define a block size of 4 subjects and determine a random permutation of 2 treatment and 2 control assignments employed the scheme in question. This is repeated to cover the request number of blocks in each stratum in order to randomize the total number of required subjects. We expect our study sample to reflect LACDHS patient population race/ethnicity stratification (9% African American and 68% Latinx).

Table 3 - Stratified Random Sampling

Block	Category	Number of participants to enroll
Block 1	African American + control	18
Block 2	African American + case	18
Block 3	Latinx + control	53
Block 4	Latinx + case	53

We will refer the control arm as “Group 1” and the intervention arm as “Group 2” for the purposes of explaining to prospective participants they will be randomly assigned to a group without compromising the integrity of the study.

Participants will need to complete the consenting process, complete a basic demographic survey, and wait to be randomly assigned to either Group 1 or 2. Once assigned to a group, the study staff will notify the participant of which group they were assigned to. The methodologies of

each respective group are detailed below after the participants are notified which group they were randomly assigned to.

Control Arm- Standard Treatment (Group 1):

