The standard care for the control arm will be: the LACDHS Vaccine Hesitancy Outreach Group calling patients once every month to remind patients of the need to be vaccinated and tested if needed. During the duration of the six weeks, the study participants will be exposed to the call from the LACDHS Vaccine Hesitancy Outreach Group.

Participants will receive two phone calls six-weeks apart, where they will complete a pre-survey in the first phone call, and 2 surveys (post-survey and CDE survey) in the second phone call. The survey will measure their trust in medical institutions, rate their self-efficacy, and intention, knowledge, and perceptions on COVID-19 testing and vaccination. Each survey will take about a half hour to complete, with the total time commitment for participants in Group 1 is about 1-1.5 hours. A copy of the surveys will be sent to the study participant either by email (preferred) or postal mail, prior to the telephone call.

An outline of the activities in Group 1 will look like:

1. Complete the pre- survey
2. Wait 6 weeks, where the LACDHS Vaccine Outreach Group will call one time in the month to remind them about getting the vaccine
3. After the 6 weeks have passed, the study staff will follow up with the participant to complete the post-survey and the CDE survey.

Study staff will use the REDCap Calendar feature to track events (such as when to administer the pre- and post- surveys) and will be used for data entry. The filters and reminders on the calendar feature assist study staff with adding events to adhere to study follow up times for study staff to call participants six-weeks later. If participants do not answer the phone calls to complete the post-survey, we will add a note on the patient’s chart, follow up three times to provide additional opportunities for patients to complete the study, and mark the patient’s chart as “Incomplete”. Once phone calls and post- surveys are complete, study staff will mark the participants’ charts as “Complete.”

Intervention Arm - CHW-led curriculum (Group 2)

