Participants assigned to the intervention group will be asked to participate in the virtual intervention, consisting of six-weekly group classes via Zoom, and six-weekly personalized teleconsultations (via phone call or Zoom) at a suitable time for both participants and CHWs. Study participants will receive 6 linguistically and ethnically concordant weekly two-hour group classes and personalized teleconsultations led by CHWs. The total time commitment for Group 2 will be a maximum of 20 hours (6 two-hour group classes, + 6 one hour personal session, + 2 half hour phone calls), over the next 6 weeks.

Table 4 outlines the group classes that will be used in the intervention. The findings from Aims 1 and 2 are incorporated in the curriculum and address the four barriers to COVID-19 testing and vaccination (mistrust, COVID-19 knowledge, social support, and health & technological literacy). The list of topic areas for the group sessions, which incorporate findings from Aim 1 and 2, were validated by the study CHWs specialists. The complete list of topics and learning goals under each module is found in **“Attachment 2 - Aim 3 Curriculum Module Outline.”** These topic areas are grouped into curricular tracks as summarized below:

Table 4: Summary of Group Classes for Intervention Arm	
Week 1	1) Introduction and Exploration CHWs will introduce process, build rapport and elicit the key needs/ concerns of the patient group (topics: previous pandemics, current pandemic, how

	current pandemic affected them)
Week 2	2) Misinformation, Information, and Prevention (topics: where do they get their news, understanding misinformation, social distancing in housing contexts with limited space, mask wearing and handwashing, contact tracing, vaccination etc.)
Week 3	3) COVID-19 Testing, and General Vaccine Information (topics: types of tests, locations and processes around testing and vaccination, fears about testing, and general vaccination information.)
Week 4	4) COVID-19 Vaccination (topics: types of vaccines, locations and processes around vaccination, fears about vaccination etc.)
Week 5	5) Building Social Support (topics: caring for a sick member of the family; managing self-isolation; social services and mental health resources; hospitalization and treatment; managing chronic illnesses, accessing specialty care, accessing telehealth-based care etc.).
Week 6	6) Closure: CHWs will ask patients to reflect on their learning and address any additional concerns

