- Have participant complete the post-survey and the CDE survey

Once there are groups of 5-8 participants assigned to the intervention arm, the groups of participants will be assigned to an Intervention CHW to start the intervention. Depending on recruitment of participants, the intervention arm start dates will be staggered.

A note for the Intervention Group:

Participants will be notified during the consent process that if they are randomly assigned to Group 2 (intervention group), then participants will need to have a reliable internet connection and a device with a screen larger than 7 inches to attend the classes.

To remove any barriers to connecting to the group classes, if participants state they do not have a large enough device to use to log into the zoom meetings, participants will be provided with an android tablet with the Zoom application installed. The study staff will not require the participants to return the tablets. The study staff do not believe giving the tablets might inflict a sense of unfairness to the participants that end up being in the control arm. It is not unfair to provide the tablets to the participants in the intervention arm for the following reasons:

1. The time commitment is different, 20 hours for intervention and up to 2 hours for the control arm.
2. Intervention arm participants need the tablet to join the classes, the control arm participants don't need a tablet to complete the activity.

In addition, the tablets would be an older model and are worth \$100 each, not an expensive device such as an iPad. The tablets would quickly lose their values and would not be able to be repurposed for another study. We believe it is best that we give the tablets to the participants so they can feel they can be trusted and it can help with participant retention in the study.

A note about the NIH's Common Data Element Survey

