Participants who are patients in medically underserved settings at risk of COVID-19 could benefit from obtaining additional information about resources and services about COVID 19 including information on how to access COVID testing or vaccinations, get additional support from CHWs, including increased technological literacy. They may also not get direct benefit. But, we have minimized the risk and have safeguards in place. The principle risk is breach of confidentiality and discomfort or anxiety in sharing information with the investigators in group and personal session, and surveys. However, we aim to minimize the risk in several ways, (e.g. limiting who has access to the data, the use of REDCap to collect data, the use of unique study ID# on the participant's data and keeping the master code list in a separate location). We have additional safeguards in place, such as regular meetings with the study team to review subject safety and data integrity, data security plan, implementing DSMP, keeping close communication with the participants, and resolving adverse events in a timely manner. Therefore, the risk to participants are reasonable in relation to anticipated benefits.

Given the unprecedented nature of the disease and severity of health outcomes related to COVID-19, there is an urgent need to increase COVID-19 testing and vaccine uptake in communities of color. The LACDHS, one of the largest safety net systems in the country, is not unique in facing declination of COVID-19 testing and vaccination in their safety net patient population. We propose that development and testing of a community engaged, CHW- based intervention could be useful for other similar safety net settings. This proposal has the primary goal of a) increasing COVID-19 testing and vaccine uptake for individual patients, and the secondary goal of b) developing a sustained public health presence in these communities to build trust and preparedness for critical future needs.

15. Therapeutic Alternatives: What therapeutic alternative(s) are reasonably available to potential participants should they choose not to participate in the study? *These may be research or non-research-based alternatives.*

This study does not involve therapy. Therefore, there are no therapeutic alternatives.

16. Risk/Benefit Ratio: What is the risk benefit ratio of this research, compared with available alternatives?

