The potential benefits of the research must justify the risks to research participants. The risk/benefit ratio of the research must be at least as favorable for the participants as that presented by standard treatments for their condition. When comparing the risk/benefit ratio of research with that of available alternatives, the alternative of doing nothing should be included in the analysis.

The risk/benefit ratio of this research is favorable, because this is a low risk study and we aim to minimize the risk in several ways, (e.g. limiting who has access to the data, the use of REDCap to collect data, the use of unique study ID# on the participant's data and keeping the master code list in a separate, secure location). While there is no direct benefit to the individual participant, there may be a benefit to society in that the information gained in the study. Findings from this study may help identify barriers to COVID 19 testing, vaccination, and health care for African American and Latino patients in the Los Angeles County Department of Health Services, which may also inform the challenges faced by African American and Latino patients in similar County health care systems in other cities. The risks to the participants are reasonable in relation to the importance of knowledge to be gained.

Financial Considerations

17. Payment for Participation: Describe all plans to compensate participants, including provision of services, and other reimbursements. Describe the conditions that participants must fulfill to receive full or partial payment.

Study participants in the case arm will receive a \$599 compensation (71 participants), and study participants in the control arm will receive \$100 compensation (71 participants) for their time and effort.

Control arm:

Participants in the control arm will be compensated with a \$100 gift card at the end of the study, after they complete the basic demographic, CDE, pre- and post- surveys. If the participant starts the surveys and cannot complete the required pre-, post-, and demographic surveys, then the participant will get the partial payment of \$50.

Case arm:

Participants will be compensated in weekly installments, after completing the first week of the 6-week program, the participant will receive a \$99 gift card, and subsequent weeks with \$100 gift cards for every successful week of completion (group session and personal session with CHW).

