Aim 3 - After data cleaning, we will assess psychometric properties of all scaled measures, calculate descriptive statistics to ensure quality of the data (check distributions, examine outliers) and to describe study participants. Bivariate analyses will include independent t-tests models (or their nonparametric equivalents, e.g. Wilcoxon rank-sum test, differences between the groups in trust and self-efficacy. Paired-tests (or Wilcoxon signed-rank test) will be used to assess change within groups. Contingency table analyses will address intention to participate in COVID-19 testing and vaccination. We will then fit multiple regression models predicting change in COVID-19 testing- and vaccine-related knowledge, trust, and self-efficacy as a function of intervention group, racial/ethnic group, and possible interactions. We will use covariate adjustment approaches such as multiple linear and logistic regression models for the three outcomes (trust, self-efficacy, intent to participate) while controlling for demographic characteristics (e.g. age, gender, education, health status) and other potential covariates that will be identified a priori. We do not anticipate many missing data, given the format of completion. However, if we do have 10% or more missing, we will impute data using SAS PROC MI and SAS PROC MIANALYZE to implement these multiple imputation procedures. With respect to sample size, with 64 subjects in each of the two study groups, it will be possible to detect an effect size of 0.5 standard deviations in a quantitative outcome (a medium effect size in Cohen’s terminology) with 80% power and 2-sided 5% significance level.

VII. Funding

4. Check all types of funding sources for this study.

 Federal Grant/Contract  State, Local Government  International	 Private  Internal Grant Program  Departmental
--	--

 Industry	 Other:
2. Name of Funding Source (e.g. NIH)	NIH/National Library of Medicine
3. Grant/Contract Title*	A Community Health Worker Intervention to Identify and Decrease Barriers to COVID-19 Testing and Vaccination among Los Angeles County Department of Health Safety-Net Patients (Title of the Supplement to parent R01)

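### Section VI.25 treats all 128 outcomes as independent, but the intervention arm is taught in CHW-led groups of 5-8, so power is overstated and standard errors are too small if outcomes correlate within groups

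*Protocol*

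**What the plan says.** All references are to the protocol.

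- **Randomisation (VI.8, Intervention Design).** Individual, 1:1, in blocks of four: "We will stratify the randomization on the basis of race/ethnicity".
- **Intervention arm (VI.8, Training of CHWs and Group 2).** After randomisation, "Once there are groups of 5-8 participants assigned to the intervention arm, the groups of participants will be assigned to an Intervention CHW". Each CHW looks after 5-8 patients. "Study participants will receive 6 linguistically and ethnically concordant weekly two-hour group classes and personalized teleconsultations led by CHWs".
- **Control arm (VI.8, Group 1).** "Participants will receive two phone calls six-weeks apart", plus the routine reminder call. Nothing is delivered in groups.
- **Sample size (VI.25 and VI.8).** "with 64 subjects in each of the two study groups, it will be possible to detect an effect size of 0.5 standard deviations", with 80% power and a two-sided 5% level. The only inflation is for dropout: "we will recruit a total of 142 patients to allow for approximately 10% attrition from each group".
- **Analysis (VI.25).** Between-arm comparisons use independent t-tests or rank-sum tests, contingency tables for intent, and multiple linear and logistic regression for trust, self-efficacy and intent. No term or variance adjustment for CHW or class group appears.
- **Reach of the conclusion (VI.14).** A tested CHW-"based intervention could be useful for other similar safety net settings".

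**The concern.** This is a partially nested design: controls are independent individuals, while intervention patients share a CHW, six classes and the same classmates. The protocol's own conceptual framework (VI.2) says the programme works through the CHW's rapport, trust-building and social support, and trust is one of the three key outcomes. Some similarity between patients of the same CHW is therefore plausible.

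If it exists, the mean of the intervention arm is less precise than 64 independent values would make it. A test that ignores this uses a standard error that is too small and gives p-values that are too small. A test that allows for it has less than 80% power. The stated 80% power and 5% level then cannot both hold.

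**Working it through.** **Inputs from the protocol.** 64 analysed per arm, difference 0.5 SD, two-sided 5% (VI.25). Groups of 5-8 in the intervention arm only (VI.8). CHWs: 3 African American and 9 Latinx, so 12 planned groups (VI.8). Intervention patients recruited: 18 + 53 = 71 (Table 3; VI.17 also gives 71).

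**Assumption.** The protocol gives no ICC. Values of 0.01, 0.02, 0.05 and 0.10 are assumed. The relevant ICC is what remains after race/ethnicity, which is a randomisation stratum and a regression term.

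**1. The protocol's own figure.** SE = √(2/64) = 0.1768, noncentrality 0.5/0.1768 = 2.83 on 126 df, power 80.15%. The stated 80% is reproduced with independent observations in both arms.

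**2. Number of groups, k.** Planned: 12 (18/3 = 6.0 and 53/9 = 5.9 patients each). Fewest possible: 71/8 = 8.9, so 9. If every class is ethnically concordant, 18/8 needs 3 groups and 53/8 needs 7, so 10. The range used is 12 to 9.

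**3. Variance with clustering in one arm.** With m = 64/k patients analysed per group,

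Var(difference) = [1 + (m − 1)·ICC]/64 + 1/64.

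Example, k = 12 and ICC 0.05: m = 5.33, design effect 1 + 4.33 × 0.05 = 1.217, variance (1.217 + 1)/64 = 0.0346, SE 0.186. The naive SE of 0.1768 is 5.0% too small. Relative to independence the variance is 2.217/2 = 1.108 times as large.

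**4. Power for 0.5 SD.** This is calculated first with 126 df, which isolates variance inflation, and then with Satterthwaite df based on k − 1 and 63. Each range runs from 12 groups to 9.

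| ICC | Naive SE too small by | Power, variance inflation only | Power, Satterthwaite df |
|---|---|---|---|
| 0 | 0 | 80.1% | 78.7-78.0% |
| 0.01 | 1.1-1.5% | 79.3-79.0% | 77.7-76.6% |
| 0.02 | 2.1-2.9% | 78.5-77.8% | 76.8-75.3% |
| 0.05 | 5.0-6.9% | 76.0-74.4% | 74.1-71.4% |
| 0.10 | 9.3-12.5% | 72.1-69.0% | 69.8-65.4% |

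The first row shows that 1.5-2.2 points (80.15 − 78.68 and 80.15 − 77.99) are the price of small-sample df and are not caused by clustering.

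**5. True size of the unadjusted 5% t-test.** Simulated with zero average effect and random group effects, 400,000 runs per case: 5.2-5.4%, 5.5-5.7%, 6.3-6.8% and 7.6-8.7% at ICC 0.01, 0.02, 0.05 and 0.10. A Satterthwaite test on group means stayed at 5.0-5.2%. With CHW effects held fixed, the unadjusted test ran at 4.5-5.0%.

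**6. What covariates could recover.** To offset the variance inflation, covariates must explain 1 − 1/1.108 = 9.8% (12 groups) to 1 − 1/1.153 = 13.3% (9 groups) of outcome variance at ICC 0.05, and 17.8-23.4% at ICC 0.10.

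**The case against.** **The harm depends on two things the protocol does not state: the ICC and the inference target.** This is true. At an ICC of about 0.02 or less the standard error is at most 3% too small and the size at most 5.7%. The reach of the conclusion is inferred from one sentence in a benefits section, about a programme that is being pre-tested. If inference is confined to the participating CHWs, or the programme changes nobody's outcome, the type I concern does not apply. But VI.25 states 80% and 5% without any such condition, and VI.14 does look beyond these CHWs.

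**The null scenario is unusual.** At ICC 0.10 the between-group SD is √0.10 ≈ 0.32. A zero average effect would then mean that some groups gain and others lose. A common curriculum, 24 hours of CHW training and feedback on encounter forms should hold that variation down. This is a fair argument for a smaller ICC, but not for zero.

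**The planned test loses little power.** At 0.5 SD the unadjusted test still rejects in about 77-80% of simulated trials. At ICC 0.05-0.10 it manages this only with an inflated error rate, and it still falls below 80%.

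**A statistical analysis plan could add a clustered model.** It could, since the regression wording is open-ended. That would not correct the power sentence or the independent tests the protocol already names.

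**Two limits stand.** The calculations cover a continuous outcome compared by t-test. For binary intent, rank tests and adjusted models the direction follows from the same reasoning, but the size was not computed. The number of CHWs in use is also uncertain: VI.8 budgets each CHW 6 hours a week of classes, although one two-hour class a week would serve one group. If some CHWs take several groups, there are fewer CHW clusters than assumed here.

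**Conclusion.** The concern holds, conditionally, and should be fixed. The 80% figure assumes independence that the delivery of the intervention does not support, and the named tests make no allowance for it. The consequence is moderate at an ICC of 0.05-0.10, where variance inflation alone costs roughly 4 to 11 points of power. It is small at 0.02 or less. These sizes rest on an assumed ICC, 9 to 12 groups, 64 analysed per arm, no covariate adjustment, and inference meant to extend beyond the participating CHWs.

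**What to change.** In VI.25, state that between-arm comparisons of trust, self-efficacy and intent allow for CHW-group clustering in the intervention arm only, with controls as singletons and small-sample df. A partially nested mixed model or a Satterthwaite test on group means would serve. For intent, name a simpler cluster-adjusted method in case a logistic mixed model is unstable with 9-12 small groups.

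Restate the power sentence over explicit assumptions, keeping the two losses apart, for example:

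> With 64 per arm, 9-12 CHW groups and an assumed residual ICC of 0.01, 0.05 or 0.10, power for 0.5 SD before covariate adjustment is about 79%, 74-76% or 69-72% from variance inflation alone, and 77-78%, 71-74% or 65-70% with small-sample df (78-79% at ICC 0).

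Record the CHW and group identifier for each intervention participant in REDCap, or confirm that the patient encounter forms already hold it. Without that identifier the clustered analysis cannot be done later.

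The cost is wording and at most one data field, with no extra patients. The downsides are a less favourable power figure, slightly wider intervals, and 1.5-2.2 points of power given up even if the ICC turns out to be zero.
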